8.2.2. Treatment Period

Following 5 days of stabilization on ≤ 4 mg BUP, on the morning of Day 1 of the Treatment Period, subjects will undergo an assessment of withdrawal symptoms (the eligibility COWS score). Randomization will occur prior to study drug dosing on Day 1. Eligible subjects will demonstrate ability to tolerate the lead-in BUP dose based upon exhibiting minimal/mild opioid withdrawal symptoms (as confirmed by COWS score ≤ 12) on Day 1. Subjects who do not qualify for randomization on Day 1 will receive Day -1 BUP dosing and complete the remaining Day -1 assessments and procedures. These subjects will then repeat Day 1 assessments and procedures on the following day, Day 1a.

The Treatment Period will consist of tapering doses of BUP (on Days 1/1a-3) in conjunction with ascending doses of oral naltrexone or PBO-N (Days 1/1a-7); see Table 3.

Table 3: ALK6428-A302 Dosing Regimen

Study Day	Group 1 Naltrexone + BUP			Group 2 Placebo-NTX + BUP		
	1st Dose NTX	2nd Dose NTX ^a	BUP ^{b,c}	1st Dose NTX	2nd Dose NTX ^a	BUP ^{b,c}
Day -5 ^d	N/A	N/A	4 mg	N/A	N/A	4 mg
Day -4	N/A	N/A	4 mg	N/A	N/A	4 mg
Day -3	N/A	N/A	4 mg	N/A	N/A	4 mg
Day -2	N/A	N/A	4 mg	N/A	N/A	4 mg
Day -1	N/A	N/A	4 mg	N/A	N/A	4 mg
Day 1	0.25 mg	0.25 mg	4 mg	PBO-N	PBO-N	4 mg

Table 3: ALK6428-A302 Dosing Regimen (Continued)

Study Day	Group 1 Naltrexone + BUP			Group 2 Placebo-NTX + BUP		
	1st Dose NTX	2nd Dose NTX ^a	BUP ^{b,c}	1st Dose NTX	2nd Dose NTX ^a	BUP ^{b,c}
Day 1a	0.25 mg	0.25 mg	4 mg	PBO-N	PBO-N	4 mg
Day 2	0.25 mg	0.25 mg	2 mg	PBO-N	PBO-N	2 mg
Day 3	0.5 mg	0.5 mg	2 mg	PBO-N	PBO-N	2 mg
Day 4	1.5 mg	1.5 mg	N/A	PBO-N	PBO-N	N/A
Day 5	3 mg	3 mg	N/A	PBO-N	PBO-N	N/A
Day 6	7.5 mg	7.5 mg	N/A	PBO-N	PBO-N	N/A
Day 7	15 mg	15 mg	N/A	PBO-N	PBO-N	N/A
Day 8	Naloxone 3.0 mg (1.5 mg + 1.5 mg) then VIVITROL			Naloxone 3.0 mg (1.5 mg + 1.5 mg) then VIVITROL		
Day 8a ^e	Naloxone 3.0 mg (1.5 mg + 1.5 mg) then VIVITROL			Naloxone 3.0 mg (1.5 mg + 1.5 mg) then VIVITROL		

N/A=not applicable; BUP=buprenorphine; NTX=naltrexone; PBO-N=placebo naltrexone

^a The second dose of naltrexone/PBO-N will be administered at least 60 minutes after the first dose of naltrexone/PBO-N, following a clinical evaluation of tolerability (based upon withdrawal symptoms).

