^b On days when subjects receive both BUP and naltrexone/PBO-N, BUP will be given sublingually immediately following the second dose of oral naltrexone/PBO-N. If a subject does not qualify for the second dose of naltrexone/PBO-N, the subject will still receive the BUP dose for that day and will be monitored in the clinic for 60 minutes following the BUP dose.

^c Subjects maintained on <4 mg at study entry will continue on their current dose until the treatment period taper calls for further decrease to establish a consistent daily dose prior to transitional dosing with naltrexone.

^d Subjects entering the BUP Lead-in Period at doses of BUP >4 mg/day will have the option, at the discretion of the study physician, to receive an additional take-home dose of BUP 2 mg on Day -5 only.

^e If a subject has a positive naloxone challenge on Day 8, he/she will not receive the VIVITROL injection, but will receive Day 7 study drug (naltrexone/PBO-N), and complete Day 7 assessments and procedures. He/she will be offered the opportunity to remain in the residential unit overnight and may repeat the naloxone challenge the following day (Day 8a) to qualify for VIVITROL administration.

[figure not shown]
The total daily naltrexone or PBO-N allocation will be split over 2 separate doses administered at least 60 minutes apart. Administration of the second naltrexone or PBO-N dose will depend upon how well the first was tolerated.

On Days 1/1a through 7, subjects will undergo a baseline COWS and SOWS assessment prior to the first dose of naltrexone or PBO-N (see [Figure 2](#)). On Day 1/1a, the eligibility COWS score may serve as the predose COWS score, if conducted within 60 minutes prior to dosing. At 30 and 60 minutes postdose, the COWS and SOWS will be re-administered. If withdrawal symptoms are stable (ie, increase of ≤ 5 points in COWS score from predose COWS) at the 60-minute assessment, the second dose of oral naltrexone or PBO-N will be administered. For these early qualifying subjects, the next COWS/SOWS assessments at 90 and 120 minutes post-first dose will constitute their post-second dose assessments.

Subjects who did not qualify for the second dose of naltrexone or PBO-N at 60 minutes will also receive the 90- and 120-minute COWS/SOWS assessments (see [Figure 2](#)), and if their withdrawal symptoms have stabilized sufficiently by 120 minutes post-first dose (ie, increase of

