8.8.11.7. Desire for Opioids Visual Analogue Scale

The desire for opioids will be measured using a 100-mm, horizontal VAS, with 0 anchored on the left representing "no desire for opioids" and 100 anchored on the right representing "strongest imaginable desire for opioids." Subjects will place a vertical line on the scale to indicate their desire for opioids at that particular time. The VAS will be self-administered at the timepoints specified in Table 4. In addition to morning and evening assessments throughout the residential period, the VAS will be self-administered during clinical testing sessions (see

Section 8.4) according to the timetable provided in [Figure 2](#). A sample can be found in [Appendix E](#).

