9.4. Randomization/Method of Assigning Subjects to Treatment

Subjects will be randomly assigned in a 1:1 ratio to 1 of 2 treatment groups: naltrexone + BUP or PBO-N + BUP, stratified according to low (<8 mg/day) vs. high (8 mg/day) BUP maintenance dose at the time of initiation of the BUP Lead-in Period. The naltrexone or PBO-N assignment will be blinded while the BUP dose will be open-label. A randomization schedule will be prepared by an independent biostatistician and uploaded into an Interactive Web Response System (IWRS). The pharmacist or designee will contact the IWRS, which will assign the subject to a treatment group according to the next available randomization record. The unblinded site pharmacist or designee will dispense naltrexone or placebo for administration to subjects.

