13.2. General Statistical Methodology

In general, summary statistics (ie, n, mean, standard deviation, median, minimum and maximum for continuous variables, and number [%] of subjects in each category for categorical variables) will be provided by treatment group for all variables.

Baseline values are defined as any nonmissing assessments prior to receiving the first dose of naltrexone or PBO-N.

Source data for the summary tables and statistical analyses will be presented as by-subject data listings.

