13.4.3. Other Secondary Endpoints

- Proportion of post-VIVITROL days (Days 9-11) in which subjects in each group demonstrate mild (COWS ≤ 12) opioid withdrawal

The analyses will be carried out using a negative binomial model with treatment as a factor.

- Mean peak COWS scores during the Treatment Period and VIVITROL Induction and Post-VIVITROL Observation Period (Days 1/1a-11)
- Area under the curve (AUC) for COWS scores during the Treatment Period and VIVITROL Induction and Post-VIVITROL Observation Period (Days 1/1a-11)
- Mean score for “desire for opioids” VAS during the Treatment Period and VIVITROL Induction and Post-VIVITROL Observation Period (Days 1/1a-11)

These endpoints will be analyzed using an analysis of variance (ANOVA), with treatment as a factor.

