13.4.4. Exploratory Endpoints

- Number and proportion of subjects in PGART response category at the end of the post-VIVITROL observation period (Day 11)

The analyses will be carried out using a logistic regression model with treatment as a factor.

- Change from baseline in pupil diameter following study drug administration during the Treatment Period (Days 1/1a-7)
- Change in frequency of substance use from screening to Day 36 assessed via the QSUI
- AUC for SOWS scores during the Treatment Period and VIVITROL Induction and Post-VIVITROL Observation Period (Days 1/1a-11)
- Change from baseline in the standardized T scores for cognitive assessments

The analyses will be carried out using an analysis of covariance (ANCOVA) with treatment as a factor.

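### Mean peak COWS, COWS AUC and mean desire-for-opioids VAS are analysed by ANOVA on treatment alone, giving up precision that collected pre-dose scores and the randomisation stratum could provide

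*Protocol*

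**What the plan says.** Protocol Section 13.4.3 lists three continuous endpoints over Days 1/1a-11: mean peak COWS, COWS AUC and the mean desire-for-opioids VAS. None is a change from baseline. The analysis is given in one sentence: "These endpoints will be analyzed using an analysis of variance (ANOVA), with treatment as a factor".

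Other sections show what is available before treatment starts:

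- **COWS.** Section 8.2.2 makes a Day 1/1a score of 12 or less a condition of randomisation ("Eligible subjects will demonstrate ability to tolerate the lead-in BUP dose based upon exhibiting minimal/mild opioid withdrawal symptoms"). It also says: "On Days 1/1a through 7, subjects will undergo a baseline COWS and SOWS assessment prior to the first dose of naltrexone or PBO-N".
- **VAS.** Section 8.8.11.7 says: "In addition to morning and evening assessments throughout the residential period, the VAS will be self-administered during clinical testing sessions". Section 8.4 starts those sessions about 15 minutes before the first dose and schedules morning and evening VAS from Day -2.
- **Stratum.** Section 9.4 randomises 1:1, "stratified according to low (<8 mg/day) vs. high (8 mg/day) BUP maintenance dose". No efficacy model in Sections 13.4.1 to 13.4.4 names this factor.
- **Baseline.** Section 13.2: "Baseline values are defined as any nonmissing assessments prior to receiving the first dose of naltrexone or PBO-N".

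Section 13.4.4 assigns ANCOVA to a group of exploratory endpoints that includes SOWS AUC over the same days.

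**The concern.** Subjects who arrive on Day 1 with more withdrawal symptoms or more craving may score higher throughout, whichever arm they are in. A model with treatment as its only term leaves that variation in the error. With about 46 subjects per arm, the intervals for these three comparisons are then wider than necessary, to the extent that baseline predicts outcome.

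The choice also sits oddly within the plan. COWS AUC and SOWS AUC have the same structure, cover the same days and both have pre-dose scores. The lower-ranked exploratory endpoint gets the adjusted method and the higher-ranked secondary endpoint the unadjusted one, with no reason given.

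**Working it through.** **The plan's own figure.** Section 13.1 gives power only for the primary endpoint: at least 90% with 46 per group, for 90% versus 60%, two-sided 5%. The pooled normal approximation gives 92.7%, so that statement is reproduced. For the three endpoints here the protocol gives no SD, effect size or correlation, so there is no stated figure to reproduce.

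**Inputs.** From the protocol: 46 per arm (N = 92) and two-sided 5%. Assumed: correlation r between baseline and outcome of 0, 0.2, 0.3 or 0.5; a reference power of 80% under ANOVA; and a stratum with no effect of its own, so that it only costs a degree of freedom.

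**Large-sample result.** Adjustment multiplies the residual variance by 1 - r², so

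power = Φ[(1.960 + 0.8416)/√(1 - r²) - 1.960].

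| r | 1 - r² | power |
|---|---|---|
| 0.2 | 0.96 | 81.6% |
| 0.3 | 0.91 | 83.6% |
| 0.5 | 0.75 | 89.9% |

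**Finite-sample result at N = 92.** ANOVA has 92 - 2 = 90 df. A standardised difference of 0.590 then gives 80% power by the noncentral t. ANCOVA with two further terms has 88 df. Chance imbalance in those terms inflates the variance of the treatment estimate on average by 1 + 2/87 = 89/87, so the variance factor is (1 - r²)(89/87). The interval-width ratio is the square root of that factor times t(0.975; 88)/t(0.975; 90) = 1.9873/1.9867.

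| r | variance factor | power | CI width, ANCOVA/ANOVA |
|---|---|---|---|
| 0 | 1.023 | 79.1% | 1.012 |
| 0.2 | 0.982 | 80.7% | 0.991 |
| 0.3 | 0.931 | 82.7% | 0.965 |
| 0.5 | 0.767 | 89.2% | 0.876 |

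The width ratio equals 1 at r = 0.152. Simulation with 20,000 trials per value of r gives power of 79.1%, 80.8%, 82.8% and 89.1%, in agreement.

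**If the stratum matters.** A separate simulation (4,000 trials, standardised difference 0.584, stratum assumed to explain 2% of the variance) gives 79.6% for ANOVA against 83.2% for ANCOVA at r = 0.3, and 79.6% against 90.2% at r = 0.5.

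**Which baseline value.** Section 13.2 admits any pre-dose assessment, and there are several: lead-in scores, morning and evening scores from Day -2, and the Day 1/1a scores. Section 8.2.2 also uses the word baseline for the pre-dose score of each treatment day. This costs the planned ANOVA nothing, but a covariate needs one value per subject, and scores from Day 2 onwards are already post-treatment.

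**The case against.** The strongest reply is that nothing is wrong. Randomisation makes the unadjusted comparison unbiased, the test is valid, and these are non-key secondary endpoints with no power claim. That stands, and it limits the point to efficiency.

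The gain may also be small. The COWS ceiling of 12 at entry narrows the baseline range for two of the three endpoints. Baseline is measured on stable buprenorphine, whereas the outcome covers its removal, naltrexone or placebo, the naloxone challenge and VIVITROL, so the first need not predict the second. Nothing in the protocol supports r = 0.5 over r = 0.2. This stands too, although VAS has no comparable entry limit.

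Finally, naming treatment as a factor does not say that it is the only one. Section 13.4.4 speaks of ANCOVA without naming a covariate, so the stratum might be added in a statistical analysis plan that is not at hand. This is fair for the stratum, which is better described as not named than as excluded. It does not reach the baseline score: a continuous covariate is contrary to the ANOVA that Section 13.4.3 specifies, so that part is a stated choice and not an open detail.

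**Conclusion.** The point holds as a recommended improvement in precision, not as an error of validity. For r between 0.2 and 0.5, adjustment narrows the intervals by about 1% to 12% and lifts an 80%-power comparison to about 81% to 89%. If baseline and stratum explain nothing, intervals are about 1% wider and power is about 79%. Adjustment pays once r exceeds about 0.15.

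These figures rest on assumed correlations and an assumed 80% reference power. For the COWS endpoints the gain may lie at the low end. Because the possible loss is about 1% and the possible gain several times that, the change is worth making. The sample size and the primary and key secondary analyses are untouched.

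**What to change.** **Section 13.4.3.** For the three endpoints, replace ANOVA with ANCOVA: treatment and buprenorphine-dose stratum (<8 versus 8 mg/day) as factors and the same-scale baseline score as covariate, that is, COWS for the two COWS endpoints and VAS for the VAS endpoint.

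**Section 13.2, supporting change.** Define baseline as the last nonmissing value of the variable before the first dose of naltrexone or placebo on Day 1/1a. For COWS and VAS this is the Day 1/1a pre-dose score. For variables last measured earlier it is the latest earlier value, for example Day -1 for the cognitive tests and screening for ECG. Keep screening as the reference for the QSUI endpoint, which Section 13.4.4 defines as "Change in frequency of substance use from screening to Day 36 assessed via the QSUI".

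**Cost.** Wording only, with no new data or visits, and two degrees of freedom (88 instead of 90). Fix the covariates before unblinding, so that the model cannot appear to have been chosen from the results.

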13.4.4. Exploratory Endpoints

- Number and proportion of subjects in PGART response category at the end of the post-VIVITROL observation period (Day 11)

The analyses will be carried out using a logistic regression model with treatment as a factor.

- Change from baseline in pupil diameter following study drug administration during the Treatment Period (Days 1/1a-7)
- Change in frequency of substance use from screening to Day 36 assessed via the QSUI
- AUC for SOWS scores during the Treatment Period and VIVITROL Induction and Post-VIVITROL Observation Period (Days 1/1a-11)
- Change from baseline in the standardized T scores for cognitive assessments

The analyses will be carried out using an analysis of covariance (ANCOVA) with treatment as a factor.

13.5. Safety and Tolerability Analyses

Safety analyses will be performed using the safety population.

Safety and tolerability will be evaluated based on AEs, vital sign and oxygen saturation measurements, laboratory test results, ECG findings and C-SSRS scores.

Reported AE terms will be coded using the Medical Dictionary for Regulatory Activities (MedDRA).

The incidence of treatment-emergent AEs will be summarized by treatment group and overall by system organ class, and preferred terms within each system organ class. SAEs and AEs resulting in treatment discontinuation will also be summarized. AEs occurring during the treatment period preceding the naloxone challenge will be analyzed separately from AEs occurring on or after the naloxone challenge day.

Change from baseline in laboratory tests, vital signs and oxygen saturation, and ECG assessments (uncorrected QT, QTcF, QTcB, HR, RR and QRS intervals) will be summarized by treatment group and overall at each visit. Number (percentage) of subjects with potentially clinically significant (PCS) values at any postbaseline visit will be also summarized by treatment group.

For each ideation/behavior type in C-SSRS, as well as the overall ideation/behavior category, the number and percentage of subjects with 'Yes' responses at any post baseline visit (including unscheduled visit) will be summarized by treatment group.

Number and percent of subjects initiating concomitant medications, including ancillary medications, during the induction period will be summarized.

Concomitant medications will be categorized and presented using the World Health Organization (WHO) drug Anatomical Therapeutic Chemical (ATC) classification system.

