Safety: Reported Adverse Events (AE) terms will be coded using the Medical Dictionary for Regulatory Activities (MedDRA) preferred terms and system organ classes. The incidence of treatment-emergent AEs will be summarized by treatment group and overall by system organ class, and preferred terms within each system organ class. Serious Adverse Events (SAEs) and AEs resulting in treatment discontinuation will also be summarized. AEs occurring during the treatment period preceding the naloxone challenge will be analyzed separately from AEs occurring on or after the naloxone challenge day.

The change from baseline in other safety parameters will be summarized by treatment group.

Concomitant medications will be categorized and presented using the World Health Organization (WHO) drug Anatomical Therapeutic Chemical (ATC) classification system.

Number and percentage of subjects initiating concomitant medications, including ancillary medications, during the induction period will be summarized.

Sample Size Considerations: The primary efficacy endpoint is the proportion of subjects who receive and tolerate VIVITROL injection on Day 8/8a as demonstrated by mild (COWS ≤ 12 or SOWS ≤ 10) opioid withdrawal symptoms following VIVITROL administration.

Assuming the proportion of subjects receiving and tolerating VIVITROL administration is 90% in Group 1 (naltrexone + BUP) and 60% in Group 2 (PBO-N + BUP), a sample size of approximately 46 subjects per treatment group will provide at least 90% power to detect a statistically significant difference between the two treatment groups at 5% level of significance in a two-sided test.

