8.2.3. Poorly Tolerated Doses

If withdrawal symptoms increase substantially after the initial dose of naltrexone or PBO-N (ie, COWS score increased >5 points from the predose COWS) and do not recede during subsequent COWS/SOWS testing (up to 120 minutes postdose), the subject will not receive the second dose of naltrexone or PBO-N, but may receive the scheduled dose of BUP, as well as ancillary medications. Following BUP administration, the subject will be observed for 60 minutes in the clinical setting. In addition to the standing regimen of ancillary medications (see [Section 8.9.2](#)), subjects may be administered additional doses of ancillary medications, as needed to alleviate any marked withdrawal symptoms (ie, total COWS score >12) not alleviated by BUP. The subject will continue all clinical testing sessions and the dosing scheduled for the following day.

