- ^f In addition to the study assessments conducted during the clinical testing sessions, vital signs will be measured each morning and evening throughout the residential period (Days -2 to 8/8a and any additional residential days, in the case of earlier admission or later discharge). Vital signs (blood pressure, heart rate, respiratory rate and body temperature) will be measured after the subject has been in a seated position for at least 5 minutes. In addition to standard vital sign measurements, clinical testing sessions on Days 1/1a to 7 will include oxygen saturation and pupillometry measurements to assess withdrawal effects in response to drug dosing. Measurements will be collected pre- and postdose as indicated in [Figure 2](#). Details regarding the timing of these assessments are provided in [Section 8.4](#).
- ^g A urine drug screen will be performed at all specified timepoints. The urine drug screen should be performed in the morning. On Days 1/1a to 7, it should be performed prior to the clinical testing sessions.
- ^h Eligibility will be confirmed prior to randomization and administration of the first dose of NTX/PBO-N.
- ⁱ Subjects not qualifying for randomization on Day 1 will receive the Day -1 BUP dose and will not receive NTX/PBO-N. Subjects not qualifying for VIVITROL on Day 8 will receive the Day 7 NTX/PBO-N dose, along with the COWS conducted for clinical safety purposes only.
- ^j Standing ancillary medication regimen begins on Day -2. In the event that a subject is admitted for the residential stay early (on Days -5, -4, or -3), the ancillary medication regimen will begin as soon as the subject becomes residential. Also, if needed for AE treatment or prophylaxis, ancillary medications may be initiated at the clinician's discretion on or after Day -5.
- ^k For subjects receiving VIVITROL on Day 8/8a, ancillary medications will be reduced as indicated in [Table 6](#).
- ^l COWS, SOWS and VAS to be recorded each morning (AM) and evening (PM) throughout the residential period (Days -2 to 8/8a) and any additional residential days, in the case of earlier admission or later discharge. On Days 1/1a to 7 the COWS, SOWS and VAS will also be administered as part of clinical testing sessions to measure withdrawal effects in response to study drug dosing. Details regarding the timing of these assessments are provided in [Section 8.4](#).

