8.9.2. Ancillary Medications

Subjects will receive ancillary medications on a standing schedule to treat symptoms of withdrawal, such as autonomic arousal, sleep disturbance, muscle tension and anxiety. Beginning on Day -2, medications listed in [Table 6](#) will be provided to subjects as a standing regimen during the residential phase of the study (see [Table 4](#)). In the event that a subject is admitted for the residential stay early (on Days -5, -4, or -3), the ancillary medication regimen will begin as soon as the subject becomes residential. If needed for AE treatment or prophylaxis, ancillary medications may be initiated at the clinician's discretion on or after Day -5. Because mild symptoms of withdrawal may be present for several days after the VIVITROL injection, subjects will continue using ancillary medications on a modified schedule (see [Table 4](#)) through Day 11 (or, for 3 days after VIVITROL injection).

Ancillary medications are commercially available and should be stored according to package insert instructions.

Table 6: Ancillary Medications

Medication	Dose Regimen	
	Days -2 to 7	Days 8/8a-11 ^a
Clonidine	0.1 mg oral tablet, 2 times a day	0.1 mg oral tablet, 1 time a day (only AM dose)
Clonazepam	0.5 mg oral tablet, 2 times a day	0.5 mg oral tablet, 1 time a day (only AM dose)
Trazodone hydrochloride	100 mg oral tablet, at bedtime	100 mg oral tablet, at bedtime

^a For subjects receiving VIVITROL on Day 8/8a, ancillary medications will be reduced on Days 9 through 11, as indicated.

Subjects will also be provided with a supply of sports hydration drink, which they will be encouraged to drink liberally.

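### Section 13.5 counts subjects initiating ancillary medications, but these are standing drugs from Day -2, so the count is essentially none or all and misses the extra doses given after randomisation

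*Protocol*

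**What the plan says.** Section 13.5 plans this summary: "Number and percent of subjects initiating concomitant medications, including ancillary medications, during the induction period will be summarized". The Synopsis repeats it: "Number and percentage of subjects initiating concomitant medications, including ancillary medications, during the induction period will be summarized". 

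Section 8.9.2 says that the Table 6 drugs (clonidine, clonazepam, trazodone) "will be provided to subjects as a standing regimen during the residential phase of the study". Footnote j to Table 4 (Section 8.7) gives the start: "Standing ancillary medication regimen begins on Day -2", or sooner if the subject is admitted early. On randomisation, Section 8.2.2 says: "Randomization will occur prior to study drug dosing on Day 1"; for subjects who do not qualify that day it moves to Day 1a.

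Section 8.2.3 covers a poorly tolerated first dose. Its condition begins: "If withdrawal symptoms increase substantially after the initial dose of naltrexone or PBO-N". On top of the standing regimen, "subjects may be administered additional doses of ancillary medications, as needed to alleviate any marked withdrawal symptoms", marked being defined as a total COWS above 12, where buprenorphine has not relieved them.

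**The concern.** The sentence names ancillary medications, so the authors evidently wanted to see their use. The measure chosen does not suit drugs that everyone is already taking. What can differ between arms because of treatment is the use of doses above the standing regimen: it occurs after randomisation and depends on how the subject responds to the blinded drug. Starting the drugs has neither property.

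Two things are at stake. First, the need for extra doses is itself a tolerability outcome, and tolerability is part of the secondary objective (Section 6.2). Second, Section 8.9.2 gives these drugs for autonomic arousal, muscle tension and anxiety among other symptoms, and COWS (Appendix C) scores pulse, sweating, restlessness and anxiety. More extra doses in one arm could therefore lower that arm's later COWS readings, and a reader of the results would want to know whether use was balanced.

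**Working it through.** The plan gives no figure for ancillary use, so there is none to reproduce. The check sets the sections side by side.

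**1. Who starts the drugs, and when.** All subjects in residence start by Day -2 (8.9.2; Table 4 footnote j). Randomisation is on Day 1 or 1a (8.2.2). Starting the standing drugs is therefore a pre-randomisation event.

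**2. Which window applies.** The protocol's named periods are the BUP Lead-in, the Treatment Period, the VIVITROL Induction and Post-VIVITROL Observation Period, and Follow-up. None is called simply the induction period. The plausible readings, for the three standing drugs at the planned 46 per arm (Section 13.1), are:

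| Reading of the period | Subjects initiating, each arm |
|---|---|
| Reaches back to Day -2 | about 46/46 |
| Begins at Day 1/1a | about 0/46 |
| VIVITROL Induction and Post-VIVITROL Observation only (from Day 8/8a) | about 0/46 |

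The word *about* allows for early admissions, whose start could fall before a Day -2 window. That too is settled before randomisation, so any difference between arms would be chance. The last reading also leaves out Days 1/1a to 7, which is when the 8.2.3 provision applies.

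**3. What the count would miss.** The protocol gives no rate of extra dosing, so the following is an assumption made only for illustration: 10% of one arm needs extra doses, and 10%, 30% or 50% of the other.

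- 46 × 0.10 = 4.6, about 5 subjects
- 46 × 0.30 = 13.8, about 14 subjects
- 46 × 0.50 = 23 subjects

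A count of subjects with doses above the standing regimen would read 5 versus 5, 14 versus 5, and 23 versus 5. The count of initiators would read the same in all three cases: none against none, or all against all.

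**4. Which endpoints are exposed.** Extra doses under 8.2.3 are for a COWS above 12. By then the day's peak has normally already passed 12, so that day's classification in the key secondary endpoint (days with peak COWS of 12 or less, 13.4.2) is already determined, and its contribution to mean peak COWS is little affected. What remains is readings later that day and on following days, hence COWS AUC over Days 1/1a to 11 (13.4.3), and the requirement of COWS at or below 12 before the naloxone challenge on Day 8/8a (8.3.1), which governs who can go on to meet the primary endpoint.

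**5. Whether better data exist.** Section 8.8.4 records drug, dose, regimen and start and stop dates at each visit, so doses above the standing regimen can be derived without new collection.

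**The case against.** The best reply is that extra dosing is not invisible. Section 12.1 makes the condition treated an adverse event whenever withdrawal requires ancillary doses beyond the standing regimen, and Section 13.5 tabulates treatment-emergent events by arm, separately before and from the naloxone challenge day. Section 13.5 also presents concomitant medications by ATC class without restricting this to initiators, and Section 13.2 provides by-group summaries and by-subject listings. A reader might infer that the trial has no planned look at whether co-treatment differed between arms; these provisions show that this goes too far. What they give is indirect: event terms, mixed with conditions treated by non-study drugs, and drug classes that every subject takes. None yields the number of subjects given extra doses or the number of doses.

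A second reply is that the count need not be fixed. Section 8.9.2 and Table 4 footnote j themselves speak of ancillary drugs being initiated at clinician discretion for adverse events, and start dates are recorded, so a site might enter an as-needed dose as a new record that then counts as initiation. This stands as a qualification. A flat statement that 0 of 92 subjects can be counted would assume both where the period begins and how sites enter as-needed doses, and the protocol settles neither.

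Third, a statistical analysis plan may hold a better table, and adjunctive medication is part of the intended approach, so analysing COWS as observed is legitimate. Both are fair. The point is confined to the measure that the protocol itself fixes, and it does not ask for COWS to be analysed otherwise than as observed.

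**Conclusion.** The point holds, as a minor one about a descriptive table. For the three standing drugs, the initiating count is essentially none or all in both arms and cannot show the extra doses allowed after randomisation. This rests on two assumptions: that sites do not log as-needed doses as new records, and that the undefined period is read in one of the ways set out above. The count keeps its value for other concomitant medications.

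A reader might also infer that COWS results are biased, or that the key secondary endpoint is masked. The documents support neither. They give no rate of extra dosing by arm, so size and direction are unknown, and the trigger above 12 leaves same-day peak measures little exposed. No endpoint, test or primary conclusion is shown to be wrong.

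**What to change.** In Section 13.5 and the Synopsis:

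- define the period as Day 1/1a to Day 8/8a;
- for ancillary medications, replace the initiating count with the number and percent of subjects, by treatment group and by day, who received at least one ancillary dose above the standing regimen, together with the number of such doses;
- keep the initiating count for other concomitant medications.

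To apply this on Day 8/8a, the table must state which standing schedule is in force: the Table 6 column heading starts the reduced schedule on Day 8/8a, while its footnote refers to Days 9 through 11. Those two need to be reconciled.

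It may be tempting to add a sensitivity analysis that sets readings after an extra dose to the highest value before it. This should not be done for the peak endpoints. A daily peak is a maximum; replacing later readings with the earlier maximum can never raise it, and lowers it if symptoms worsened after the dose.

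The cost is one descriptive table from data already recorded, with no change to treatment, visits or the primary analysis.
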